**Study Title: Impact of Sustained Release d-Amphetamine on Choice Between Cocaine and a Non-Drug Reinforcer**

**NCT number: NCT02383043**

**Version date: 12/17/17**

## 1. BACKGROUND

Cocaine-use disorders continue to be a significant public health concern, yet no effective pharmacological treatments have been identified. This project is founded on the proposition that translational research on the development of cocaine pharmacotherapies will benefit from the use of coordinated and homologous procedures in animals and humans to study effects of candidate medications on choice between cocaine and a non-drug reinforcer. The present application describes the human laboratory side of the project; the non-human primate research will be conducted by our colleagues at Virginia Commonwealth University. Despite the relative strengths of human and non-human primate approaches, translational research has been hampered by the use of widely different self-administration procedures and medication treatment regimens. The proposed project seeks to harmonize rhesus monkey and human procedures used to screen medications by establishing parallel self-administration methods that will employ the same cocaine doses, route of cocaine (i.e., intravenous) administration and schedule of reinforcement, as well as a species-specific alternative reinforcer that effectively reduces drug taking. Self-administration procedures will be used in this project because the reinforcing effects of drugs are central to their abuse and the development of dependence. An alternative reinforcer to cocaine will be offered because the choice to use cocaine to the exclusion of other behaviors is a hallmark of dependence, and an effective medication should assist patients in reducing drug use and reallocating behavior from drug use to more responsible and productive activities. Maintenance treatment studies are proposed to more closely model a clinical scenario. Achieving the aims of this project will exert a sustained and powerful impact by establishing a research platform for cocaine medication screening that will tightly link animal and human approaches thereby accelerating translational research on medications development.

## 2. OBJECTIVES

The primary objective of this study is to assess self-administration of cocaine vs. a non-drug reinforcer during maintenance on an indirect dopamine agonist, d-amphetamine, in an effort to equilibrate cross-species sensitivity and to provide a comparator for effects of other, non-dopaminergic candidate medications examined in future studies. Multiple d-amphetamine doses will be tested to ensure the functional equivalence of the cocaine and alternative reinforcer magnitudes, which can be further refined, if necessary, prior to testing novel compounds. d-Amphetamine was chosen as a standard because the effects of cocaine have been attributed primarily to blockade of dopamine uptake, and dopaminergic agonists alter laboratory cocaine self-administration in a predictable manner.

## 3. STUDY DESIGN

A double blind, placebo-controlled, within-subjects design will be used. Each subject will be enrolled as an inpatient for 33 days and participate in 12 experimental sessions in which the reinforcing effects of various doses of IV cocaine (0, 3, 10 and 30 mg/70 kg) and an alternative monetary reinforcer (\$6.00) will be determined on a concurrent PR schedule choice procedure during maintenance on oral d-amphetamine SR (0, 30 and 60 mg/day).

## 4. STUDY POPULATION

We intend to enroll eighteen (6 female, 12 male) completers into this study. These individuals must be English-speaking, English-reading volunteers 18-55 years of age of varying ethnic backgrounds. Enrollment in this study will occur between January 1, 2015 and December 31, 2017. Volunteers will be required to provide legal proof of age.

### *Inclusion Criteria:*

- Recent cocaine use via the smoked or intravenous route, verified by a cocaine-positive urine sample.
- Otherwise healthy, without contraindications to cocaine.
- Meet Cocaine Dependence or Abuse criteria, verified by Structured Clinical Interview for DSM-IV (SCID).

-Use of an effective form of birth control (e.g., birth control pills, surgical sterilization, IUD, cervical cap with a spermicide, condoms or abstinence; females only). A urine pregnancy test will be conducted before the start of each session to ensure that female subjects do not continue in the study if pregnant.

*Exclusion Criteria:*

- Chemistry values or screening outcomes including outside normal ranges that are deemed by the study physician to be clinically significant. Lipid levels, which have not typically been included in our screening tests, are included in this protocol as an additional check for cardiovascular health.
- Hypertension  $\geq 140/90$  mmHg during screening or before dosing on the medical safety session
- BMI  $\geq 30$ .
- Electrocardiogram abnormalities, including:
  - Atrial premature beats ( $\geq 2$  consecutive)
  - Ventricular premature beats (Lown's Grade 3 or higher;  $\geq 2$  consecutive beats, multiform)
  - Heartblock (2nd or 3rd degree AV block or bundle branch block)
  - Pre-excitation syndromes (Wolff-Parkinson-White or Lown-Ganong-Levine)
- History of serious physical disease, current physical disease, impaired cardiovascular functioning, chronic obstructive pulmonary disease, history of seizure, or current or past histories of serious psychiatric disorder that in the opinion of the study physician would interfere with study participation.
- First degree family member with significant premature cardiac comorbidity.
- Current or past histories of substance abuse or dependence that are deemed by the study physician to interfere with study completion.

Screening procedures for all subjects will include a medical history questionnaire, laboratory chemistries (blood chemistry screen, complete blood count, ECG and urinalysis) and a brief psychiatric examination. These procedures will be conducted under our lab's screening protocol (03-0509). All study participants will be judged by the study physicians, Drs. [name], [name], [name], or their representative, to be healthy.

During the initial screening interview, potential volunteers will be asked to provide a urine specimen that will be screened for the presence of recent use of amphetamine, benzodiazepines, barbiturates, cocaine, tetrahydrocannabinol (THC) and opiates. In order to continue participation once experimental sessions have begun after admittance to the hospital, volunteers must provide a urine negative for amphetamines, benzodiazepines, barbiturates and opiates on each day of their participation. Volunteers will be allowed to continue if they test positive for cocaine. Volunteers will be maintained on a caffeine free diet and will have to abstain from alcohol for the duration of their participation.

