## 7. RESEARCH PROCEDURES

*General Procedures.* Volunteers that meet the inclusion criteria will participate as inpatients at the University of Kentucky Clinical Research Unit (CRU). Volunteers will be discharged upon completion of the entire protocol.

This experiment will require each volunteer to participate for 33 days. Sessions will be conducted as outlined in Table 1 (see below). Please note three important points relating to the table below: 1) The sequence of maintenance conditions and the cocaine and d-amphetamine maintenance doses are illustrative. The order of d-amphetamine SR maintenance will be random, with one exception. The lower active d-amphetamine SR maintenance condition will be tested prior to the higher active condition. The cocaine dose order available for self-administration will be randomly determined. 2) Please also note that participation will require a minimum of three additional sessions to avoid experimental testing on weekends. More than three additional sessions might be required depending on the day of the week that a subject is admitted to the unit. 3) If subjects leave the protocol for a reason unrelated to study procedures (e.g., a family emergency or dental problems), they may be re-admitted with physician approval to complete the remainder of the protocol, picking up with the next maintenance condition after the last one completed. Thus, they may not complete the protocol over one approximately 33-day admission.

To confirm equivalent maintenance dosing across species, blood will be drawn from the indwelling catheter used for drug administration on the first and last of the four experimental sessions during each maintenance phase in order to determine plasma levels of d-amphetamine. If necessary due to trouble with the catheter, the blood sample will be drawn directly with a needle and syringe. Samples will be processed and stored by the BAL/CCTS and then shipped to the ARUP laboratories at the University of Utah for analysis using liquid chromatography / mass spectroscopy (LC/MS). Samples submitted for analysis will not contain any PHI.

Day	Table 1
1	Admission to the CRU and practice session.
2	Medical Safety Session. Start d-amphetamine maintenance in PM.
3-11	d-Amphetamine SR maintenance (30 mg daily). Oral dose administered twice daily (0700 and 1900 h) in escalating fashion, based on clinical dosing recommendations, up to target daily dose (i.e., doses 1-3 = 5 mg, doses 4&5 = 10 mg, remaining doses = 15 mg).

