8-11	Self-administration sessions. Subjects complete 1 sample and 9 choice trials to receive cocaine (0, 3, 10 and 30 mg/70 kg) or money (\$6.00) by responding on the concurrent PR schedule.
12-20	d-Amphetamine SR maintenance (placebo; 0 mg administered twice daily).
17-20	Self-administration sessions. Details are the same as Days 10-13.
21-29	d-Amphetamine SR maintenance (60 mg daily). Oral dose administered twice daily (0700 and 1900 h) in escalating fashion up to target daily dose (i.e., doses 1-3 = 5 mg, doses 4&5 = 10 mg, doses 6&7 = 20 mg, remaining doses = 30 mg).
26-29	Self-administration sessions. Details are the same as Days 10-13.
30	Discharge from the CRU.

During their participation in the research protocol, volunteers will not be allowed to leave the CRU, nor will visitors be allowed. Research volunteers will be allowed to make local telephone calls. After completing the

research protocol, interested volunteers will be offered a referral to an appropriate drug abuse treatment program.

All volunteers will provide urine and expired air samples daily during study participation once experimental sessions have been initiated. The presence of non-nicotine, non-cannabinoid drugs of abuse or alcohol not administered experimentally in the research protocol will result in immediate termination from the research study.

This experiment will consist of 12 experimental sessions across approximately 33 days and conducted according to the timeline in Table 1 (see above). On the day of admission, volunteers will be allowed to acclimate to the CRU. During this time, volunteers will be maintained on a caffeine-free diet, receive instructions concerning the details of the daily research procedures and general rules of the inpatient research unit and complete a "practice" session to familiarize them with the experimental routine and tasks. The practice session will follow the session timeline with the exception that no drug or response-contingent money will be available and no maintenance dose will be administered. On the day after the practice session, subjects will participate in a medical safety session in which they will receive each of the doses IV cocaine that will be available in subsequent sessions (i.e., 1 infusion of 0, 3, 10 and 30 mg/70kg cocaine) administered in ascending order and separated by 30-min intervals; subjects exceeding the predetermined cardiovascular parameters will be excluded from further participation.

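### The continuation rule in section 4 requires an amphetamine-negative urine every day, although every subject is assigned d-amphetamine, and it contradicts the termination rule in section 7

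*Protocol*

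**What the plan says.** Two places in the Protocol govern what a positive urine means after admission.

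- **Section 4, Study Population (the paragraph after the eligibility criteria).** After describing the screening urine test, the text turns to the inpatient stay. The condition begins "In order to continue participation once experimental sessions have begun after admittance to the hospital" and continues that "volunteers must provide a urine negative for amphetamines, benzodiazepines, barbiturates and opiates on each day of their participation". The next sentence adds one express permission: "Volunteers will be allowed to continue if they test positive for cocaine". THC is on the screening panel but not on the must-be-negative list, so it is tolerated by omission. Study d-amphetamine is not mentioned.
- **Section 7, Research Procedures (the text after Table 1).** Daily urine and breath samples are required once sessions have started. Nicotine and cannabinoids are set aside, and the rule is that the presence of other "drugs of abuse or alcohol not administered experimentally in the research protocol will result in immediate termination".

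On the drug itself, section 3 describes a within-subjects design with oral d-amphetamine SR maintenance at 0, 30 and 60 mg/day. Table 1 in section 7 describes active maintenance as "Oral dose administered twice daily (0700 and 1900 h) in escalating fashion". The drug-dose paragraph of section 7 states that steady-state blood levels are reached before the self-administration sessions start.

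**The concern.** Section 4 makes the absence of amphetamines a daily condition of continuing in a trial whose maintenance drug is an amphetamine. It does deal with one study drug, cocaine, by permitting a positive result. It gives the other study drug no such permission, so the plain reading is that an amphetamine positive ends participation whatever its source.

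Section 7 says the opposite for a positive that comes from protocol dosing. Staff therefore have two rules for the same test result. Keeping a subject in under section 7 is a departure from section 4 as written, and removing the subject under section 4 takes out someone for complying with assigned treatment. A rule that decides who stays in a within-subjects trial should have one reading.

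**Working it through.** The plan gives no figure to reproduce here. The check compares the two rules and counts the sessions they affect.

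**Step 1. Does the section 4 rule apply during treatment, or only at screening?** Its opening words place it after hospital admission and after sessions have begun, and it applies on each day. It is separate from the screening test in the sentence before it. It therefore covers the active phases.

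**Step 2. Is there an exemption for study d-amphetamine?**

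| Urine result | Section 4 | Section 7 |
|---|---|---|
| Cocaine | Expressly permitted | Permitted if administered experimentally |
| THC | Not on the must-be-negative list | Excluded from the rule (cannabinoids) |
| Benzodiazepines, barbiturates, opiates | Cannot continue | Terminate |
| Amphetamine, non-study source | Cannot continue | Terminate |
| Amphetamine, study dosing | Cannot continue | May continue |

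The two rules agree on benzodiazepines, barbiturates and opiates, on THC, on study cocaine and on non-study amphetamine. They give opposite answers in the last row. No other section adds an amphetamine exemption to section 4 or says that section 7 takes precedence.

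**Step 3. How much of the trial lies in that last row?** Inputs: three maintenance conditions (section 3), two of them active, and four experimental sessions per maintenance phase (section 7, General Procedures).

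- Total sessions: 3 × 4 = 12, which matches the 12 stated in section 3.
- Sessions in active phases: 2 × 4 = 8.
- Share: 8 / 12 = 67%.

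The only constraint on order is that 30 mg/day comes before 60 mg/day. The permitted orders are therefore 0-30-60, 30-0-60 and 30-60-0, and the count is 8 of 12 in each.

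**Step 4. Would study drug be present when urine is tested?** Active dosing is twice daily, steady state is claimed before sessions begin, and Table 3 puts urine drug testing at 0700 on session days. The drug is therefore expected to be on board. Whether the panel would read positive depends on the assay, which the Protocol does not describe. The conflict in wording does not depend on the assay; how often it would arise in practice does.

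**The case against.** The strongest reply is that no one could sensibly misapply this. Maintenance on d-amphetamine is the purpose of the study. Section 7 is the operative procedure and excludes experimentally administered drugs in terms. Section 10 (Safety Precautions) gives the aim of urine monitoring as checking that subjects keep to the drug-use restrictions, and swallowing the assigned capsules breaks no restriction. On this view section 4 means non-study amphetamine and lacks only an obvious qualifier.

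Most of that stands. It is very probably the intent, and it is why the point is minor. It does not remove the contradiction. Section 4 takes the trouble to permit one study drug and is silent on the other, and nothing ranks section 7 above it. Nor is this something left to a statistical analysis plan: a continuation rule belongs in the protocol, and here the protocol states it in two incompatible ways.

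A reader might go further and infer that no subject could ever complete the trial. That needs both a literal application of section 4, which section 7 shows was probably not meant, and an assay that detects d-amphetamine at these doses, which the Protocol does not state. Any count of stopping days or doses taken would also lean on Table 1, whose sequence and doses are described as illustrative and whose timetable shifts to avoid weekend sessions. The documents do not support that conclusion.

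A reader might also infer that a positive urine would unblind the study. The Protocol does not say who sees the results. It also states that collection of the self-administration, subjective-effect and physiological data is automated (section 17, Data Monitoring Plan). That inference is too conditional to carry a finding.

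**Conclusion.** The concern holds as an internal inconsistency of minor severity. Section 4, as written, bars continuation for any amphetamine positive caused by the study drug, in a design where 8 of 12 sessions fall in active phases, and it contradicts section 7 on exactly that case. Confidence in the conflict of wording is high because it rests on the text alone. The practical consequence rests on the further assumption that the urine panel detects study d-amphetamine, and it is limited because section 7 supplies a workable rule. Sample size, alpha and the planned analysis of variance are untouched.

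**What to change.** In section 4, insert *(other than study-administered d-amphetamine)* directly after the word amphetamines in the must-be-negative list. The rule then agrees with section 7, and both study drugs are covered in the same place. Nothing else needs to change.

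The amendment is one clause and adds no procedure. Its downside is that a positive amphetamine screen during an active phase cannot separate study drug from illicit use, so this test will not reveal illicit amphetamine use in those phases. That risk is limited, since section 7 does not allow inpatients to leave the unit or receive visitors.

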## **5. SUBJECT RECRUITMENT METHODS AND PRIVACY**

Volunteers are recruited primarily through formal advertisement (i.e., regular newspaper advertisements placed generally in free newspapers), local flyers posted in public areas (e.g., bars, marketplaces) and by word-of-mouth. These advertisements are approved under our screening protocol (IRB # 03-0509). Volunteers will make initial contact by phone with one of our recruiters who have completed the research training and HIPAA compliance web-based teaching models. If the volunteer self-discloses information that would make him/her potentially eligible for the study, they will be invited to come in for a screening appointment. Screening is completed by one of our research assistants at the UK Laboratory of Human Behavioral Pharmacology (LHBP). Study investigators may interact with volunteers in this setting and appropriate cautions are in place to ensure privacy during the intake process.

## **6. INFORMED CONSENT PROCESS**

All potential subjects that are identified using the subject recruitment methods noted above will provide informed consent prior to participating in the protocol. Subjects that meet the eligibility criteria noted above will come to the LHBP and will undergo a field sobriety test and provide an expired air sample that will be tested for the presence of alcohol. If the subject passes the field sobriety test (walk and turn, one-leg balance [timed], finger-to-nose and backwards-counting tasks) and the expired air sample is negative, he or she will then be

given a copy of the approved informed consent document to read and sign. After reading the consent document, the PI or one of the Co-Is on this protocol will address any questions the subject may have in order to assess the subject's understanding of the protocol. After this, the subject will receive a copy of the informed consent document and will sign a form indicating that they have received a copy of the form they read and signed.

## 7. RESEARCH PROCEDURES

*General Procedures.* Volunteers that meet the inclusion criteria will participate as inpatients at the University of Kentucky Clinical Research Unit (CRU). Volunteers will be discharged upon completion of the entire protocol.

This experiment will require each volunteer to participate for 33 days. Sessions will be conducted as outlined in Table 1 (see below). Please note three important points relating to the table below: 1) The sequence of maintenance conditions and the cocaine and d-amphetamine maintenance doses are illustrative. The order of d-amphetamine SR maintenance will be random, with one exception. The lower active d-amphetamine SR maintenance condition will be tested prior to the higher active condition. The cocaine dose order available for self-administration will be randomly determined. 2) Please also note that participation will require a minimum of three additional sessions to avoid experimental testing on weekends. More than three additional sessions might be required depending on the day of the week that a subject is admitted to the unit. 3) If subjects leave the protocol for a reason unrelated to study procedures (e.g., a family emergency or dental problems), they may be re-admitted with physician approval to complete the remainder of the protocol, picking up with the next maintenance condition after the last one completed. Thus, they may not complete the protocol over one approximately 33-day admission.

To confirm equivalent maintenance dosing across species, blood will be drawn from the indwelling catheter used for drug administration on the first and last of the four experimental sessions during each maintenance phase in order to determine plasma levels of d-amphetamine. If necessary due to trouble with the catheter, the blood sample will be drawn directly with a needle and syringe. Samples will be processed and stored by the BAL/CCTS and then shipped to the ARUP laboratories at the University of Utah for analysis using liquid chromatography / mass spectroscopy (LC/MS). Samples submitted for analysis will not contain any PHI.

Day	Table 1
1	Admission to the CRU and practice session.
2	Medical Safety Session. Start d-amphetamine maintenance in PM.
3-11	d-Amphetamine SR maintenance (30 mg daily). Oral dose administered twice daily (0700 and 1900 h) in escalating fashion, based on clinical dosing recommendations, up to target daily dose (i.e., doses 1-3 = 5 mg, doses 4&5 = 10 mg, remaining doses = 15 mg).
8-11	Self-administration sessions. Subjects complete 1 sample and 9 choice trials to receive cocaine (0, 3, 10 and 30 mg/70 kg) or money (\$6.00) by responding on the concurrent PR schedule.
12-20	d-Amphetamine SR maintenance (placebo; 0 mg administered twice daily).
17-20	Self-administration sessions. Details are the same as Days 10-13.
21-29	d-Amphetamine SR maintenance (60 mg daily). Oral dose administered twice daily (0700 and 1900 h) in escalating fashion up to target daily dose (i.e., doses 1-3 = 5 mg, doses 4&5 = 10 mg, doses 6&7 = 20 mg, remaining doses = 30 mg).
26-29	Self-administration sessions. Details are the same as Days 10-13.
30	Discharge from the CRU.

During their participation in the research protocol, volunteers will not be allowed to leave the CRU, nor will visitors be allowed. Research volunteers will be allowed to make local telephone calls. After completing the

research protocol, interested volunteers will be offered a referral to an appropriate drug abuse treatment program.

All volunteers will provide urine and expired air samples daily during study participation once experimental sessions have been initiated. The presence of non-nicotine, non-cannabinoid drugs of abuse or alcohol not administered experimentally in the research protocol will result in immediate termination from the research study.

This experiment will consist of 12 experimental sessions across approximately 33 days and conducted according to the timeline in Table 1 (see above). On the day of admission, volunteers will be allowed to acclimate to the CRU. During this time, volunteers will be maintained on a caffeine-free diet, receive instructions concerning the details of the daily research procedures and general rules of the inpatient research unit and complete a "practice" session to familiarize them with the experimental routine and tasks. The practice session will follow the session timeline with the exception that no drug or response-contingent money will be available and no maintenance dose will be administered. On the day after the practice session, subjects will participate in a medical safety session in which they will receive each of the doses IV cocaine that will be available in subsequent sessions (i.e., 1 infusion of 0, 3, 10 and 30 mg/70kg cocaine) administered in ascending order and separated by 30-min intervals; subjects exceeding the predetermined cardiovascular parameters will be excluded from further participation.

Cardiovascular hypersensitivity is defined as heart rate  $> (220 - \text{subject age}) \times 0.85$ , systolic pressure  $> 180$  mm Hg or diastolic pressure  $> 120$  mm Hg. ECG. If vital signs are elevated above these criteria, the nurse or physician will re-assess using the automated machine at minute intervals for 5 total readings. If vital signs remain above these criteria for all 5 readings, a manual reading will be taken. If vital signs are still elevated, a subject will not receive further doses, will be followed until symptom resolution, and will be excluded from further research participation. These criteria have been recommended by [name]., who served as an advisor in the preparation of this protocol, and used in previous studies of intravenous cocaine self-administration in humans (e.g., Walsh et al., 2010). Cardiovascular hypersensitivity also includes prolonged abnormal heart rhythmicity assessed via 3-lead telemetry. Abnormal heart rhythmicity during experimental sessions is defined as ventricular arrhythmias that occur at a frequency greater than 5 per minute, are multifocal, or occur as couplets (2 consecutive beats) or salvos (3 or more consecutive beats), and persist for greater than 15 min. A cardiovascular emergency will be managed using UK medical center procedures (i.e., response from a code blue team). In [name] previous study at the CRU that guided the medical safety monitoring parameters for the present protocol, subjects were administered up to 320 mg/70 kg intravenous cocaine across an experimental session (i.e., maximum of 8 administrations of 40 mg/70 kg). Important to note is that none of the subjects (N=22) were discharged due to exceeding the cardiovascular threshold criteria. One subject experienced premature ventricular contraction after receiving placebo and active cocaine, and was subsequently discharged. Cocaine produced expected increases in heart rate and blood pressure, but there were no clinically significant changes that required cessation of cocaine dosing or protocol discharge. Likewise, no subjects have been discharged from the ongoing protocol in which subjects self-administer various doses of IV cocaine (0, 3, 10 and 30 mg/70 kg) due to cardiovascular adverse events.

Maintenance dosing with d-amphetamine will begin on the evening of the medical safety session according to the dose escalation procedure described in Table 1. Maintenance medications will not be administered if a subject's heart rate is  $\geq 100$  bpm, systolic pressure is  $\geq 150$  mmHg or diastolic pressure is  $\geq 100$  mmHg. In addition, the UKU side effects scale will be completed daily to monitor for the emergence of side effects and HR/BP will be taken every two hours while subjects are awake. The timeline for daily activities on maintenance days is shown in Table 2.

Time	Table 2-Daily Activities for Maintenance Days
0700	Patient awakened. Vital signs recorded. Medication administered if vitals are within range. Subject eats breakfast.
1200	Lunch is served.
1300	UKU completed.
1900	Dinner is served. Vital signs recorded. Medication administered if vitals are within range and no indication of sedation or withdrawal.
2300	Lights out.

Prior to each experimental session, subjects will be allowed to eat a standard, fat-free breakfast. Breakfast must be consumed by 0800 (a minimum of 2 hours prior to the first scheduled dose at 1000). Table 3 (below) outlines the experimental session activities. Sessions will begin at 0900 hours and will last approximately 6 hours. At 0900 hours, volunteers will complete the pre-drug measures and cardiovascular monitoring will begin. The first intravenous drug administration (Sampling Dose) will occur at 1000 h and subjects will be informed of the alternative reinforcer available that session. A behavioral assessment battery (subjective questionnaires) will be completed immediately before and 15 min after dosing. At 1030 subjects will be offered the opportunity to complete the first ratio on the concurrent PR task to receive the cocaine dose sampled previously or the money value available that session. A dose earned will be provided immediately after completion of the response requirement. Subjects will have the opportunity to request that items not available on the UK CRU be purchased for them using money earned. Nine total choice trials will occur at 30-min intervals (i.e., 1030, 1100, 1130, 1200, 1230, 1300, 1330, 1400 and 1430 h). The behavioral assessment battery will be completed prior to each choice trial. No experimental activities will be scheduled for the remainder of the day. Volunteers will be free to engage in recreational activities (e.g., watch television, read, listen to music, arts and crafts, play video or board games). Research volunteers will be required to be in bed with the lights out by 2300 hours.

Heart rate and blood pressure will be recorded prior to cocaine administration and at frequent intervals (i.e., every 2 minutes) afterwards for the duration of the session. Prior to cocaine administration, subjects must have a heart rate of < 130 bpm, systolic blood pressure < 165 mm Hg and diastolic blood pressure < 100 mm Hg. Heart rhythmicity will be assessed via 3-lead telemetry continuously during each experimental session, will be printed out and verified as normal prior to dose administration, and will be monitored continuously for a minimum of 15 minutes following each infusion.

Time	Table 3 Experimental Session Timeline
0700	Subject awakened and provided with breakfast. Urine drug testing. Subjects allowed a single tobacco cigarette prior to the start of experimental activities (smoking after session activities permitted).
0900	Session begins. Cardiovascular monitoring initiated (see below for details).
1000	Sample dose of IV cocaine (0, 3, 10 or 30 mg/70 kg) administered; subjects informed of alternative monetary value available that session. Behavioral assessment battery (subjective questionnaires) completed immediately before and 15 min after dosing.
1030	Subjects complete the first ratio on the concurrent PR task to receive the sampled cocaine dose or the money value available that session. A dose earned will be provided immediately after completion of the response requirement. Subjects will also have the opportunity to request that items not available on the UK CRU be purchased for them using these earnings. Nine total choice trials will occur at 30-min intervals (i.e., 1030, 1100, 1130, 1200, 1230, 1300, 1330, 1400 and 1430 h). The assessment battery will be completed prior to each choice trial.
1500	Session ends. Subjects free to engage in various recreational activities.

*Apparatus.* Behavioral testing will be conducted at the CRU. Volunteers will be tested using an individual Macintosh computer that automates behavioral tasks. When not completing behavioral tasks, volunteers will be allowed to engage in sedentary recreational activities (i.e., read or watch television).

*Progressive-Ratio Procedure.* We have used similar PR procedures to assess the reinforcing effects of stimulant drugs, including cocaine (reviewed in [name], 2008; [name] et al., 2010). After sampling the IV cocaine dose (3, 10 and 30 mg/70 kg) and being informed of the money value available in that session, subjects will complete 9 choice trials, separated by 30 min. The initial response requirement for each reinforcer will be 400 responses (i.e., mouse clicks). The completion of a response requirement for a given reinforcer (i.e., cocaine or money) will increase the response requirement for that reinforcer by 100. These response requirements were based on our previous human laboratory studies that have tested various ratio parameters in an effort to maximize drug-maintained responding while minimizing placebo self-administration (Sevak et al., 2011; [name] et al., 2010). Subjects may choose not to complete a ratio for either reinforcer during a choice trial, but physiological measures and the assessment battery will still be completed as scheduled, and the ratio requirements for each reinforcer will carry forward to the next trial.

*Subject-Rated Drug-Effect Questionnaires.* Two questionnaires used extensively in human behavioral pharmacology research will be used to measure various aspects of mood and drug effect: 1) Adjective-Rating Scale and 2) Drug-Effect Questionnaire. The subjective-effects measures are described in Appendix A.

*Physiological Indices.* Heart rate, blood pressure and heart rhythmicity (*via* ECG) will be recorded using a Dinamap digital monitor (Critikon, Pro 1000, Tampa, FL). These measures will be measured at least three times in the hour before intravenous drug administration and immediately prior to completion of subject-rated measures for the remainder of session. ECG monitoring will be continuously conducted, and will be printed and read immediately before, and 15 minutes after intravenous drug administration, during the experimental session. Telemetry-certified nurses will interpret the results with instructions to contact Drs. [name], [name] or [name] regarding abnormalities.

*Drug Dose and Administration.* Cocaine and d-amphetamine doses will be administered under double-blind conditions and medical supervision. We currently hold an IND for intranasal cocaine administration and have amended it for IV administration during d-amphetamine maintenance.

Syringes containing the IV cocaine dose for a particular session (i.e., dose in mg/70kg) will be drawn from aseptically prepared stock solutions. Stock solutions are prepared by dissolving cocaine HCl USP (Mallinckrodt, St. Louis, MO) in 0.9% sodium chloride, and filtering the solution through a 0.22  $\mu$ m filter into a sterile, pyrogen-free vial. The doses for administration (3, 10 and 30 mg/70 kg) will be prepared and drawn up into syringes within 24 h of an experimental session and individually labeled for each subject. The 0 mg dose will contain only 0.9% sodium chloride. Each dose will be administered in a standard volume (e.g., 1.0 mL) via a catheter in the non-dominant arm over 30 s. A slow drip of normal saline will be used after initial catheter insertion for the duration of the session to maintain patency and a 10 mL normal saline flush will be administered after each cocaine injection. This method of cocaine preparation has been conducted previously at the UK Investigational Pharmacy, and this procedure for IV administration has been used successfully in our ongoing study.

d-Amphetamine SR doses will be prepared using commercially available tablets and cornstarch placed into size 0 opaque capsules. Placebo capsules will contain only cornstarch, but will be visually identical to active dose capsules. d-Amphetamine maintenance doses will be administered in an escalating fashion up to the target daily dose (e.g., doses 1-3 = 5 mg, doses 4&5 = 10 mg, doses 6-final = 15 mg for the 30 mg/day dose; doses 1-3 = 5 mg, doses 4&5 = 10, doses 6&7 = 20 mg, doses 8-final = 30 mg for the 60 mg/day dose). Target doses are based on clinical dosing recommendations and a 12-h half-life (Spansule® sustained-release d-amphetamine product information), which will result in the attainment of steady-state blood levels prior to initiating cocaine self-administration sessions. We have safely and successfully used this dose escalation procedure in previous protocols (e.g., Pike et al., 2014).

*Data Analysis.* Self-administration data from the 8 subjects who complete the protocol will be analyzed using two-factor repeated-measures ANOVA with Cocaine Dose (0, 3, 10 and 30 mg/70 kg) and d-Amphetamine SR Maintenance Dose (0, 30 and 60 mg/day) as factors. A significant attenuation in the cocaine self-administration dose-effect curve will be inferred if the main effect of d-Amphetamine or an interaction of the

Cocaine and d-Amphetamine factors attains statistical significance in the ANOVA, and the mean square error term will be used to conduct contrast tests to make appropriate pair-wise comparisons between means. Subjective-effects and physiological data from the Sampling Trial will be analyzed in a similar fashion.

